3.4 Assignment to Study

All subjects with documented consent will be assigned a unique subject number.

All subjects who satisfy the eligibility criteria will be randomly allocated to one of three treatment groups (FDY-5301 at 1 mg/kg or 2 mg/kg, or volume-matched placebo).

Confidential Page 25 of 64

4 SELECTION AND WITHDRAWAL OF SUBJECTS

4.1 Inclusion Criteria

Subjects who meet all of the following criteria will be eligible to participate in the study:

- 1. Age 18-75 years
- 2. Major trauma defined as:
 - a. thoracic and/or abdominal and/or pelvic injury
 - b. necessitating admission to ICU with ventilation anticipated for at least 24 hrs
 - c. hemorrhagic shock defined as systolic blood pressure (SBP) <90 mmHG requiring blood transfusion or base deficit of at least 6 mEq/L pre-hospital arrival or within one hour after hospital arrival
- 3. IRB/IEC-approved consent obtained within 48 hours of first hospital arrival time (i.e., in case of transfers, use time of arrival to first hospital immediately post injury)

4.2 Exclusion Criteria

Subjects who meet any of the following criteria will be excluded from participation in the study:

- 1. Likely to die within 48 hrs from time of screening
- 2. Any neurological condition that is perceived at the time of hospital admission as an immediate threat to life or incompatible with good functional recovery and where early limitation or withdrawal of therapy is being considered. For example:
 - Computed tomography imaging showing evidence of traumatic brain injury (TBI), combined with best representative Glasgow Coma Score (GCS) Motor Score ≤4 at approximately 24 hrs post injury
- 3. Evidence of nonreversible spinal cord injury
- 4. Bilateral femoral fractures
- 5. Women who are pregnant or breastfeeding. Women of reproductive potential must have a negative serum pregnancy test prior to randomization.
- 6. Known thyroid disease or thyroid disorder, including subjects on thyroid hormone replacement therapy at the time of randomization
- 7. Known allergy to iodine
- 8. Chronic renal disease requiring dialysis
- 9. Body mass index (BMI) >40 kg/m² or <16 kg/m²
- 10. Body weight (BW) >140 kg (or >309 lb)
- 11. History or presence of debilitating neurologic or other neuromuscular disease (e.g., spina bifida, amyotrophic lateral sclerosis, multiple sclerosis) at time of randomization

Confidential Page 26 of 64

- 12. Current metastatic cancer
- 13. Solid organ transplant recipient
- 14. Evidence of pre-existing sarcopenia defined as having a pre-trauma Clinical Frailty Score (CFS) of ≥5 (see Appendix 7: Clinical Frailty Score) or based on clinical judgement (e.g. frail by appearance, cachexia, etc.)
- 15. Use of systemic corticosteroids, immunomodulators, or oncologic chemotherapy within 6 months of randomization (inhaled and topical steroids are allowed)
- 16. Use of investigational drugs or devices within 30 days of randomization
- 17. Any clinically significant abnormality identified prior to randomization that in the judgment of the Investigator or Sponsor would preclude safe completion of the study, or confound the anticipated benefit of FDY-5301

4.3 Screen Failures

Screen failures are defined as subjects for whom consent to participate in the clinical study is obtained but who are not subsequently randomized. A minimal set of screen failure information is required and will be captured on study case report forms (CRFs).

Individuals who are consented but do not meet the criteria for participation in this study (screen failure) may not be rescreened.

4.4 Subject Discontinuation of Investigational Product Administration

Subjects who receive at least 1 dose of IP and are subsequently discontinued from further IP administration (e.g., due to toxicity) will not be withdrawn from the study.

Subjects will remain on study and continue to have all scheduled evaluations through the Month 6 visit per Section 5, Study Schedule.

Administration of the IP to a subject may be discontinued for any of the following reasons:

- Adverse event
- Investigator decision
- Sponsor decision
- Subject or subject's representative decision
- Hospital discharge prior to Day 7

Subjects who discontinue IP will not be replaced.

4.4.1 Renal Failure

Subjects who develop acute renal failure, whether or not they begin dialysis treatment, do not require discontinuation of IP administration.

If a subject requires dialysis, unscheduled plasma PK samples (US sites only) will be collected pre- and post-dose of each IP administration while on dialysis.

Confidential Page 27 of 64

4.5 Subject Withdrawal from the Study

All randomized subjects should remain on study and continue to have all scheduled evaluations through the Month 6 visit per Section 5. A subject may be withdrawn from the study for any of the following reasons:

- Withdrawal of consent
- Study termination by Sponsor
- Lost to follow-up

Whenever possible, subjects withdrawing from the study should undergo a final visit, to include those assessments noted for the Day 28 visit (or Month 6 visit if Day 28 visit was completed).

The term "withdrawal of consent" should be used only when the subject (or the subject's legally authorized representative) no longer wishes to participate in the trial and no longer authorizes the Investigators to follow the subject.

Withdrawal of consent for follow-up should be accompanied by documentation of the reason for withdrawal. Withdrawal of consent for treatment should be distinguished from withdrawal of consent for follow-up visits and from withdrawal of consent for non-subject contact follow-up, e.g., medical records checks. When consent is withdrawn, subjects should be explicitly asked about the contribution of possible adverse events to the decision to withdraw consent, and any adverse event information elicited should be documented. Preferably, the subject should withdraw consent in writing and, if the subject (or the subject's legally authorized representative) refuses or is physically unavailable, the site should document the reason for the subject's failure to withdraw consent in writing. In the event that consent is withdrawn, the study site may consult public records, such as those establishing survival status of the subject.

Subjects who withdraw from the study will not be replaced.

4.6 Subjects Lost to Follow Up

If the subject fails to respond to requests for follow-up, the clinical trial site will send a registered letter or equivalent, at a minimum, to the subject requesting contact with the clinic. All attempts to resume contact (including copies of written correspondence) will be included in the source documentation. Subjects who do not respond to requests for follow-up after all reasonable attempts to establish contact will be considered "lost to follow-up".

Subjects who are lost to follow-up will not be replaced.

Confidential Page 28 of 64

5 STUDY SCHEDULE

The schedule of assessments for all clinical trial sites is listed in Table 1. The additional schedule of assessments for US clinical trial sites only is listed in Table 2.

All study visits will be calculated from time of first IP dose (Day 1). Month 3 and Month 6 visits will be calculated based on the calendar month (e.g., if Day 1 is February 15th, Month 3 would be May 15th and Month 6 would be August 15th).

Confidential Page 29 of 64

Table 1: Schedule of Assessments

Activity	Screening		In-Hospital										Follow Up Long Term Follow Up			
	J			Day 2ª	Day 3ª	Day 4ª	Day 5ª	Day 6ª	Day 7ª	Day 10ª	Day 14ª			Day 28 If Discharged Earlier	Month 3	Month 6
			(+/-) 24hrs of 1 st IP dose								(+/-) 1 day	(+/-) 1 day	(+/-) 1 day	(+) 2 weeks	(+/-) 1 week	(+/-) 2 weeks
Informed Consent	X											,				
Eligibility Criteria	X															
Estimated Height & Weight	X															
Medical History	X															
Demographics	X															
Physical Examination	X				X				X		X	X	X			
Serum Pregnancy Test	X															
Safety Laboratory Tests	X				X				X		X	X	X	X		
12-lead ECG		Randomization	XcXq		X				X		X		X			
TRISS		izat	X													
IP Administration		E	Χe	Χ ^f	Χ ^f	Χ ^f	Χf	Χ ^f	Χf							
CT Scan of Abdomen	Xa	pue								Xh						
SOFAi		8	X		X		à à		X		X	X	X			
Sit to Stand	26									Х	X	X	X		O.	
СРАх			X		X				X	Х	X	X	X			
MRC-SS							à à		å f				X			
Barthel Index													X		X	X
SF-36v2 Health Survey									à f				X		X	Х
Organ Dysfunction TTR			X	X	X	X	X	X	X	X	X	X	X			
Time of Extubation			X	X	X	X	X	X	X	X	X	X	X		DA .	
Occurrence of Sepsis			X	X	X	X	X	X	X	X	X	X	X			
Discharge & Disposition	2		X	X	X	X	X	X	X	X	X	X	X		X	Х
General Health Inquiry															X	X
Overall Survival	. 00		X	X	X	X	X	X	X	X	X	X	X	χj	X	X
Concomitant Medications	X		X	X	X	X	X	X	X	X	X	X	X	χj		
Adverse Events	X		X	X	X	X	X	X	X	X	X	X	X	χi		1

^aIf being discharged from hospital prior to Day 28, conduct all "Day 28 or Hospital Discharge if Earlier" assessments

ⁱConducted until ICU discharge only

^jMay be conducted by phone

Page 30 of 64

^bAssessments may be conducted up to 2 days prior to discharge if earlier than Day 28

^cUp to 12 hrs pre-dose

d Up to 4 hrs post-dose

^eAs soon as possible and within 48 hrs of FIRST hospital arrival time (i.e. immediately post injury)

f(+/-) 4 hrs using the time of day of first IP dose

^gOnly if performed as standard of care within 48 hrs of first hospital arrival and up to 24 hrs after first IP dose

^hOnly if still in hospital at Day 10 (+/-) 3 days and screening abdominal CT was performed as standard of care

Table 2: Additional Schedule of Assessments

US Sites Only

Activity	Screening		In-Hospital											Follow Up	Long Term	Follow Up	
														Day 28 If			
		_	_											Day 28 or Hospital	Discharged		
		tion	Day 1	Day 2k	Day 3 ^k	Day 4 ^k	Day 5 ^k	Day 6k	Day 7	Day 10	Day 14	Day 21	Discharge if Earlier	Earlier	Month 3	Month 6	
		iza	(+/-) 24hrs of 1 st IP dose								(+/-)	(+/-)	(+/-)	(+)	(+/-)	(+/-)	
56	100	lon	of 1st IP dose								1 day	1 day	1 day	2 weeks	1 week	2 weeks	
Plasma PK	- PG - CO	and	XIXm		X^lX^m				X^IX^m						PG 08		
Unscheduled Plasma PK ⁿ	100	8		X^IX^m		X^IX^m	X^IX^m	$X^{I}X^{m}$							98		
Blood Biomarkers	100		Xº		X				X						Cit		
Leukocyte Gene Expression	OR .		Xº						X						Cité		

kIf being discharged from hospital prior to Day 7, conduct all Day 7 assessments

Page 31 of 64

¹Up to 4 hrs pre-dose

^mUp to 4 hrs post-dose

[&]quot;If a subject requires dialysis, unscheduled plasma PK samples will be collected pre- and post-dose of each IP administration while on dialysis

^{°(-) 24} hrs up to (+) 4 hrs of first IP dose

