1 INTRODUCTION

1.1 Disease Setting

ICU-acquired weakness (ICUAW) is characterized by peripheral muscle weakness and wasting for which no other cause can be identified besides the acute illness or its treatment (Hermans 2015, Needham 2012, Stevens 2009, Puthucheary 2013), which has been observed to last from a few weeks to years. ICUAW may be a major part of a long-term, post-intensive care syndrome (PICS) described as physical, mental and cognitive dysfunction, which extends beyond the acute hospitalization and has a major impact on the quality of life of the growing population of ICU survivors (Needham 2012). ICUAW is associated with diminished life expectancy 12 months post-discharge (Hermans 2015).

The profound inflammation and oxidative stress that occurs during critical illness leads to early depletion of many endogenous antioxidants; for example, lower circulating concentrations of tocopherol and ascorbate in association with increased concentrations of oxidized glutathione in the plasma of critically ill patients have been documented (Friedrich 2015, Goode 1995, Marshall 2007, Bertrand 1989, Metnitz 1999, Borrelli, 1996). De-iodination of thyroid hormones to release free iodide may be a beneficial endogenous reaction to injury, however the reducing capacity of that free iodide will be exceeded by anything beyond a modest injury.

FDY-5301 is designed to provide immediate and bioavailable supra-physiological concentrations of iodide, which is a potent reducing agent. In particular, it acts to catalytically degrade hydrogen peroxide; this differs from other agents which themselves are oxidized in the reaction with peroxide. The hypothesis, supported by clinical and preclinical data, is that FDY-5301 will therefore ameliorate the systemic inflammatory response and consequent tissue damage and immune dysfunction that follow major trauma, with benefits to tissues, including muscle, that are injured downstream of the initial traumatic injury.

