1.5 Justification for Dose

The selected dosing regimen for FDY-5301 is 1 or 2 mg/kg daily for 7 days and is based on the available safety, efficacy and PK modeling data for FDY-5301.

FDY-5301 is expected to provide clinically significant exogenous reducing capacity when administered to major trauma ICU patients. The systemic inflammatory response which triggers a catabolic state occurs very early following major trauma, but is postulated to last for longer than a day, and perhaps weeks following trauma (Pedroso 2012). For this reason, and given the poor outcomes expected in the ICUAW population, 7-day dosing is proposed to provide reducing capacity for a period long enough to potentially confer clinical benefit. Daily dosing is based on the half-life of FDY-5301 in healthy volunteers of 6 to 8 hours, implying a return to baseline levels after 24 hours.

Up to 10 mg/kg IV of FDY-5301 has been given to healthy volunteers in a phase 1 study without adverse effects, and a single IV bolus dose of 2 mg/kg was well tolerated in the phase 2 AMI reperfusion study in acutely ill subjects. Specifically, thyroid function tests showed similar group means across all groups, with no suggestion of a drug effect. In a published study of healthy volunteers, cumulative doses of 14 mg/kg of sodium iodide (given as daily oral doses of 1 mg/kg for 14 days) were well tolerated. (Robison 1998).

In nonclinical safety testing, the NOAEL in a rat 14-day repeat dose GLP toxicity study was 74 mg/kg/day and the NOAEL in a GLP dog 7-day repeat dose study was 20 mg/kg/day. These data support daily dosing in subjects at the high dose in this study of 2 mg/kg for up to 7 days.

The PK profile of FDY-5301 has been well characterized in humans. Following IV administration, a rapid maximal concentration (C_{max}) occurs, followed by rapid initial clearance from plasma, a terminal half-life of 6 to 8 hours, and trough levels approaching zero at 24 hours. Exposure will be adequate for daily administration without accumulation, even in subjects with renal impairment.

Confidential Page 21 of 64

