- Medical Outcomes Study Questionnaire Short Form 36v2 Health Survey (SF-36v2) and activities of daily living questionnaire (Barthel Index) at Day 28 or hospital discharge (whichever occurs first), Month 3, and Month 6
- Proportion of subjects who can complete any sit-tostand maneuver and the number of sit-to-stand maneuvers completed in 30 seconds at Days 10, 14, 21, and Day 28 or hospital discharge, whichever occurs first
- Individual organ dysfunction TTR until Day 28

In a subset of subjects:

- Blood metabolic, inflammatory, and biochemical markers of muscle damage analysis at Days 1, 3, and 7
- Plasma iodide concentrations evaluated up to 4 hrs pre- and post-dose on Days 1, 3, and 7
- Leukocyte gene expression analysis at Days 1 and 7
- Percent change from baseline in the level of the 3rd lumbar (L3) vertebra Skeletal Muscle Index (SMI) and other muscle volume measures based on Computerized Tomography (CT) scan at Day 10

[figure not shown]
Confidential Page 23 of 64

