8.4 Preparation and Administration

The formulation has no preservative and is intended for single use only. Injection solutions will be prepared using aseptic technique and inspected prior to administration. The solution for injection is a clear, colorless solution with no particulate matter.

Preparation of the administered dose will be achieved by adjusting the volume of undiluted solution (calculation is based on IP concentration of 7.2 mg/mL) according to treatment assignment. Dosage is based on the subject's body weight (estimated or actual) at screening.

IP will be administered intravenously by a healthcare professional by bolus injection over no more than 10 minutes. Use of an infusion pump is acceptable provided it can administer the total volume in less than 10 minutes. IP may be administered through a central line as long as the line is flushed prior to and following injection. IP must be administered without mixing with any other IV drugs.

Confidential Page 39 of 64

The first IP administration must occur as soon as possible and within 48 hours of first hospital arrival time (i.e. in case of transfers, use time of arrival to first hospital immediately post injury) and then daily for up to 7 days at approximately the same time each day (±4 hours using the time of day of the first IP administration).

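### The only Day 1 biomarker and gene-expression samples may be drawn up to 4 h after the first bolus, so some subjects may have no pre-treatment research sample

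*Combined protocol and SAP*

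**What the plan says.** Section 2 lists two exploratory endpoints measured on research blood in a subset of subjects: "Blood metabolic, inflammatory, and biochemical markers of muscle damage analysis at Days 1, 3, and 7" and "Leukocyte gene expression analysis at Days 1 and 7". Section 6.1.14 and Table 2 limit these samples to US sites.

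Table 2 marks one Day 1 sample for each. Footnote o applies to both and gives the window as minus 24 "hrs up to (+) 4 hrs of first IP dose". The screening column holds no research sample. The Day 3 and Day 7 tubes carry no timing relative to that day's dose.

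Other measurements are handled differently. Plasma PK in Table 2 has separate pre-dose and post-dose samples on Days 1, 3 and 7 (footnotes l and m). The Day 1 ECG in Table 1 is likewise split into a pre-dose and a post-dose recording (footnotes c and d).

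On the drug itself, Section 8.4 has it given "by bolus injection over no more than 10 minutes", Section 1.1 says that "FDY-5301 is designed to provide immediate and bioavailable supra-physiological concentrations of iodide", and Section 1.5 describes a rapid maximum "followed by rapid initial clearance from plasma, a terminal half-life of 6 to 8 hours, and trough levels approaching zero at 24 hours".

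On analysis, Section 10.2.4.3 allows continuous exploratory variables to be analysed by analysis of covariance or analysis of variance and names no covariate.

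**The concern.** The Day 1 tube is the only scheduled research sample that could serve as a pre-treatment reference. Footnote o allows it to be drawn when the subject has already received the bolus and iodide exposure is high. A subject sampled in that part of the window has no pre-treatment value for the research panel. For gene expression, with two samples in all, nothing from before treatment remains. A missing pre-dose sample cannot be recovered at analysis.

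The consequence depends on how Day 1 is used. If it enters a change score or an adjusted model, any early effect of the drug sits in the reference value in the active arms and not in placebo. Where the early effect runs in the same direction as the later one, the estimated contrast at Day 3 or Day 7 is pulled toward zero.

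**Working it through.** The plan states no figure that depends on this window, so there is nothing to reproduce. The check has three parts.

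**1. The window.** Its length is 24 + 4 = 28 h, of which 4 h lies after the dose: 4 / 28 = 14%. This does not estimate the share of subjects sampled post-dose. Section 12.3 requires consent before any study procedure, and dosing is to start as soon as possible, so the usable pre-dose time may be much shorter than 24 h.

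**2. Exposure after the dose.** Input: terminal half-life of 6 to 8 h (Section 1.5). Fraction of the terminal-phase level remaining at time t = 2^(−t / half-life).

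| Time | Half-life 6 h | Half-life 8 h |
|---|---|---|
| 4 h | 2^(−4/6) = 0.63 | 2^(−4/8) = 0.71 |
| 24 h | 2^(−24/6) = 0.06 | 2^(−24/8) = 0.125 |

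Section 1.5 also describes rapid initial clearance, so 63% to 71% is an upper guide and not a fraction of the peak. These figures concern iodide, not the markers.

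**3. Effect on a Day 1-referenced contrast.** Let δ be the true effect at the later day, q the share of active-arm subjects whose Day 1 sample is post-dose, and r the share of δ already present in that sample (same direction). Placebo has no shift. The mean active-minus-placebo difference at Day 1 is then q × r × δ, and

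contrast in change from Day 1 = δ − q × r × δ = δ × (1 − q × r).

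In an analysis of covariance with slope b on the Day 1 value, the same step gives δ × (1 − b × q × r). The change-score result is thus the larger attenuation whenever b lies between 0 and 1.

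The documents give neither q nor r. With assumed values, the share of the true contrast that remains (1 − q × r) is:

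| | r = 0.1 | r = 0.25 | r = 0.5 |
|---|---|---|---|
| q = 0.25 | 0.975 | 0.938 | 0.875 |
| q = 0.5 | 0.95 | 0.875 | 0.75 |
| q = 1 | 0.90 | 0.75 | 0.50 |

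Shrinkage therefore runs from 2.5% to 50% over this assumed grid, and it is zero if r = 0 or if Day 1 is not used in the analysis.

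**The case against.** The strongest reply is that no stated analysis is damaged. The plan never labels the Day 1 research samples as baseline. Among the exploratory endpoints, only the CT muscle measure is defined as a change from baseline, and Section 6.1.14 describes gene expression in terms of the response to trauma. Placebo subjects provide a concurrent randomized reference at every time point, so comparing Day 3 or Day 7 values without Day 1 adjustment is not biased by footnote o. Section 10 leaves detail to a separate SAP whose text is not part of the document reviewed, so a rule for post-dose Day 1 samples can be neither confirmed nor excluded. All of this stands, and it makes the bias conditional.

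Exposure is also not effect. A reader might infer from Section 1.1 that an immediate anti-inflammatory action is claimed. The word there describes iodide concentrations, and nothing in the documents shows a change in these markers within 4 h. That stands too.

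The screening safety laboratory tests include some related analytes, such as lactate dehydrogenase, aspartate aminotransferase and white cells with differential (Appendix 2). They give partial pre-randomization information but do not replace the research panel, and they include no gene expression.

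Finally, the 4 h allowance is a plausible tolerance where the first dose is urgent. This explains the window, but it does not require a late sample to be treated as equivalent to a pre-dose one.

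**Conclusion.** The point holds as a low-severity design improvement. As written, the schedule can leave a subject with no pre-treatment research sample and, for gene expression, with both samples taken after treatment began.

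Attenuation follows only if three conditions hold together: Day 1 is used as a reference or covariate, the markers respond within 4 h, and the early effect runs in the same direction as the later one. Its size is then up to q × r, about 2.5% to 50% over assumed values.

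Two stronger readings are not supported. One is that the Day 3 and Day 7 contrasts will shrink toward no effect; that takes as given an analysis and an early marker response that the plan does not state. The other is that untimed Day 3 and Day 7 tubes hide a dose response. The terminal-phase arithmetic implies an 8- to 16-fold spread in iodide over 24 h (1/0.125 to 1/0.0625), but the documents do not link that spread to noise in the markers.

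The endpoints are exploratory and US-only. No power figure, significance level, or primary or secondary conclusion depends on them.

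**What to change.** - Change footnote o so that the Day 1 biomarker and gene-expression tubes are drawn within the 24 h before the first dose, ideally with the pre-dose PK sample already scheduled for these subjects, and without delaying dosing.
- Record each draw time relative to the dose.
- Keep any Day 1 sample drawn after the bolus, but analyse it as post-dose and exclude it from any baseline adjustment. State this in the SAP, together with whether Day 1 is used as a covariate.
- Optionally, draw the Day 3 and Day 7 tubes with the existing pre-dose PK samples to standardise timing.

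The cost is a footnote and laboratory-manual change, with no extra venipuncture when the tubes are taken with the PK draw. The downside is that a few Day 1 reference values will be lost when the first dose is urgent.
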